the treatment according to the cluster of ICU they are assigned. Post-randomization pairing scheme will be employed to form the pairs if the stopping criterion is not reached at the time that first 60 outcomes have been observed. As the hospital administration changed the room type to accommodate the decrease of COVID patients (e.g., some negative pressure rooms were changed to non-negative pressure rooms), we currently recruitment included more patients in the prophylactic dose group than those of the intermediate dose group. Pending the approval of DSMB, in each ICU and each room type, we will randomize “intermediate dose rooms” and “prophylactic dose rooms” in a 3:1 ratio until we reach enrollment of 30 patients for one group and we will then only assign patients to the other group until we achieve the recruitment of 30 patients that group as well. After we recruit 30 patients for each arm, the ratio of the rooms will be changed back to 1:1 (intermediate vs. prophylactic) for the subsequent recruitment.

Success tallies:

Each time the follow-up for each patient in a pair is complete and a “good” or “poor” outcome is determined for each based on the composite primary outcome, the pair becomes “observed” and is available for sequential monitoring by adding to a running tally of the “good” outcomes for each intervention. These *success tallies* are used for the stopping rule.

Stopping and Decision rule: The criterion for stopping is a *difference of 4 or more between the tallies* if this occurs at or before 60 patients’ outcomes have been observed. At that time, intervention with the largest success tally is selected as the preferred intervention. However, we will not stop the procedure and make a decision before the outcomes of the first 60 patients have become available. In addition, if the criterion for stopping has not been reached at or before 100 outcomes have been observed, the trial will stop by *truncation* with a maximum of 100 patients. At that time, intervention with the largest success tally is selected as the preferred intervention. If there are ties for the largest success tally at time of truncation, we will select the intervention according to other considerations (safety, better secondary outcomes, etc.).

Incomplete pairs:

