where $X_i^{(n)}$ and $X_j^{(n)}$ are the observed success tallies for the selected and not selected intervention and where p_i and p_j are the respective true success probabilities. We will also calculate the likelihood of the observed success tallies under the assumption that we erred in our selection and that the true success probabilities are those for the two interventions *transposed*, namely, $L(p_j, p_i | X_i^{(n)}, X_j^{(n)})$. The *likelihood ratio* LR is the ratio of these two likelihoods. It can be shown that LR , equals the true odds ratio raised to the fourth power,

$$LR = \frac{L(p_i, p_j | X_i^{(n)}, X_j^{(n)})}{L(p_j, p_i | X_i^{(n)}, X_j^{(n)})} = \left(\frac{p_i/(1-p_i)}{p_j/(1-p_j)} \right)^4,$$

in the case where the trial ends meeting the selection criterion. In the case of truncation, the exponent 4 is replaced by $X_i^{(n)} - X_j^{(n)}$. We will evaluate LR at the maximum likelihood estimates of p_i and p_j , which are the adjusted sample proportions $(X_i^{(n)} + 0.5)/(n+1)$ and $(X_j^{(n)} + 0.5)/(n+1)$.

The values of success tallies used in LR are those used in the selection criteria, i.e., without data from incomplete pairs. However, for the values of p_i and p_j used in LR , we will use the corresponding sample proportions using *all* of the available outcome data including data from incomplete pairs. The LR may offer strong evidence of correct selection (if $LR > 10$) or only weak evidence, and the LR weight of evidence will be taken account of in evaluating whether or not to mount a subsequent phase 3 trial.

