For instance, suppose we stop after 60 patients. If the difference between the two groups' success tallies is exactly equal to 4 (the minimum given the design), the likelihood ratio (LR) in favor of having selected the truly better treatment as opposed to having made a mistaken selection equals the odds ratio (OR) raised to the 4th power. Thus, at the design alternative $p_1=0.35$, $p_2=0.20$, the LR would be 21.5. This is usually considered "very strong" evidence. Likelihood ratios in excess of 8 or 10 are generally considered to be moderate to strong evidence [Royall R. Statistical Evidence: A likelihood paradigm. 1997 Chapman and Hall/CRC]. For comparison, the usual "significant at $p < 0.05$ " corresponds to a LR of only 6.8 in large samples. Furthermore, if the design alternative holds, it is highly probable the difference between success tallies will be greater than 4. For example, if the tallies are 11 (about 30×0.35) and 6 ($=30 \times 0.20$), the LR under the design alternative is much larger (46), very strong evidence in favor of a correct selection.

To address the weight of evidence in favor of the maximum likelihood estimate (*mle*) being the true parameters as opposed to the *null* hypothesis $p_1=p_2$ being the true parameters, the generalized LR is 11.2 for the case $T=60$, $X_1=20$, $X_2=10$, which would again be moderate to strong evidence. On the other hand, if $X_1=14$, $X_2=10$, $LR=1.55$, very weak evidence against the null hypothesis. Assuming the trial does not stop at $T=60$, the above LR's will be assessed with the data at the time of selection at the observed *mle*'s for weight of evidence in favor of correct selection and for weight of evidence against the null hypothesis. The assessments will be repeated when all data have been observed, including overrun data coming in after the time of selection.

Minimizing Selection Bias

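### The likelihood-ratio formula fixes the exponent at 4 for every criterion stop, which is wrong when the lead at 60 patients exceeds 4, and two 60-patient examples are 50-per-arm values

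*Combined protocol and SAP*

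**What the plan says.** All places are in section VIII of the combined protocol and SAP.

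- **Stopping and Decision rule.** The trial stops on a "difference of 4 or more between the tallies", and no decision is made before 60 outcomes are available. It is truncated at 100 patients.
- **Formula to Calculate the Likelihood Ratio and its Interpretations, formula.** The LR is the ratio of the likelihood at the two success probabilities to the likelihood with them transposed. It is then equated to the odds ratio to the power 4 "in the case where the trial ends meeting the selection criterion. In the case of truncation, the exponent 4 is replaced by" the difference in tallies. The probabilities are replaced by adjusted proportions, (X + 0.5)/(n + 1), computed from all outcome data, including incomplete pairs. An LR above 10 is labelled strong evidence, and the LR is to be weighed when a phase 3 trial is considered.
- **Same section, first example (stop after 60 patients).** The fourth power is tied to the case where the difference between the groups' "success tallies is exactly equal to 4 (the minimum given the design), the likelihood ratio (LR) in favor of having selected" the better arm is being computed. The text adds that "if the design alternative holds, it is highly probable the difference between success tallies will be greater than 4". For 11 against 6 it says that "the LR under the design alternative is much larger (46), very strong evidence in favor of a correct selection".
- **Same section, evidence against the null.** "the generalized LR is 11.2 for the case $T=60$, $X_1=20$, $X_2=10", and then "if $X_1=14$, $X_2=10$, $LR=1.55$, very weak evidence against the null hypothesis".
- **Table 1 notes.** 60 patients means 30 in each arm.

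**The concern.** The formula names truncation as the only case in which the exponent is the observed lead. But the criterion is a lead of at least 4, and the first look comes only after 60 outcomes, by which time the lead may be well above 4. The example that follows uses the observed lead, so formula and example disagree on the one kind of stop where the choice matters.

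The two generalized LRs also do not fit the sample size they are given for.

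What is at stake is the reported weight of evidence. The plan makes the LR its main summary for the full sample and an input to the phase 3 decision. A prespecified measure should have one definition, and its worked examples should reproduce.

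**Working it through.** **1. The exponent.** Write the plan's likelihood with n per arm and divide it by its transposed form:

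LR = [p_i^X_i (1−p_i)^(n−X_i) p_j^X_j (1−p_j)^(n−X_j)] / [p_j^X_i (1−p_j)^(n−X_i) p_i^X_j (1−p_i)^(n−X_j)] = OR^(X_i − X_j),

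where OR = [p_i/(1−p_i)] / [p_j/(1−p_j)]. This holds for every outcome. It equals OR^4 only if the lead is exactly 4.

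**2. The plan's own figures.** At the design alternative, OR = (0.35/0.65)/(0.20/0.80) = 2.1538.

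- OR^4 = 21.52, the plan's 21.5 for a lead of 4.
- OR^5 = 46.35, the plan's 46 for 11 against 6. The formula's rule would give 21.5 here, because 11 against 6 at 30 per arm meets the criterion.
- At the adjusted proportions, 11 against 6 gives OR = (11.5/19.5)/(6.5/24.5) = 2.223. Exponent 4 gives 24.4 and exponent 5 gives 54.3.

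**3. How often the closed form is wrong.** After 60 patients the lead moves by at most one per pair, so every later criterion stop has a lead of exactly 4. Only stops at 60 are affected. I enumerated the design exactly: independent outcomes, 30 per arm, then pair by pair to 50 per arm, no overrun. For scenario 1 this gives an expected total of 68.4 (Table 1: 68.4), a stop at 60 in 62.6% (62.6%), correct selection 95.2% (95.1%) and truncation 10.4% (10.2%).

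| True success rates | Stop at 60 | Stop at 60 with lead above 4 | Share of stops at 60 | Median understatement over all stops at 60 |
|---|---|---|---|---|
| 0.35 / 0.20 | 62.6% | 50.6% | 80.7% | 9.1-fold |
| 0.30 / 0.20 | 46.6% | 33.8% | 72.6% | 3.6-fold |
| 0.20 / 0.20 | 25.6% | 14.5% | 56.4% | 2.4-fold |

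The understatement factor is OR^(lead − 4) at the adjusted proportions, counting a lead of exactly 4 as 1.

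**4. Thresholds.** Without overrun, the smallest OR^4 at 30 per arm with a lead of 5 or more is that for 18 against 13: [(18.5/12.5)/(13.5/17.5)]^4 = 1.919^4 = 13.5. Such a result is above 10 under either exponent, so the probabilities of exceeding 8 and 10 are the same under both: 77.8% and 70.7%; 66.7% and 59.6%; 50.9% and 45.9% in the three scenarios.

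With overrun this no longer holds. Take a stop at 13 against 8, then one more patient per arm, a failure in the leading arm and a success in the other. The tallies in the exponent stay at 13 and 8, but the proportions use 31 per arm: OR = (13.5/18.5)/(9.5/22.5) = 1.728. Exponent 4 gives 8.9; exponent 5 gives 15.4. The result falls on different sides of 10.

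**5. The generalized LRs.** The formula is L(X_1/n, X_2/n) / L(p, p), with p = (X_1 + X_2)/(2n).

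- 20 against 10, n = 30: log LR = 40 ln(2/3) + 20 ln(1/3) − 60 ln(1/2) = −16.219 − 21.972 + 41.589 = 3.398, so LR = 29.9.
- 14 against 10, n = 30: LR = 1.746.
- n = 50: 11.198 and 1.553, which round to the printed 11.2 and 1.55. Neighbouring sizes do not match both (49: 11.44 and 1.557; 51: 10.98 and 1.549).

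Adjusted proportions hardly move these values: 29.8 and 1.745 at n = 30. The prose below Table 1 shows the same pattern. It gives 82.5% for stopping with 30 per arm where the table has 62.6%, and an exact calculation at 50 per arm gives 82.5%. Text left over from a design with a first look at 50 per arm would explain both, but that is an inference.

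**The case against.** The plan defines the LR as the ratio of two likelihoods; the fourth power is offered only as a consequence. The example that follows covers a stop at 60, ties the fourth power to a lead of exactly 4, expects larger leads, and works 11 against 6 correctly. An analyst who follows the definition or the example gets the right number.

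That much stands. A reader might infer from the table that about half of trials would report a wrong LR under the design alternative. The documents do not support this: 50.6% is how often the closed form is wrong, not a predicted rate of misreporting. The objection does not remove the error, though. The formula is stated as an equality for every stop on the criterion, with truncation the only exception, and the plan's own 46 contradicts it.

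The generalized LRs are illustrations only, and no rule uses them. Their verbal gradings also survive: 29.9 is at least as strong as the text says, and 1.75 is still very weak.

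It could also be said that only the label is wrong and the examples belong to 100 patients. For 14 against 10 that would work, since a lead of 4 at the fiftieth pair is a reachable stop and 1.55 is right there. For 20 against 10 it would not: the trial would have stopped when the paired lead reached 4, so those paired tallies cannot arise at 50 per arm.

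**Conclusion.** Wrong as written, and minor. The closed form fails for stops at 60 with a lead above 4 and conflicts with the worked example in the same section. The two generalized LRs are wrong for 30 per arm.

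Two stronger readings should be resisted. First, the fixed exponent does not exaggerate the evidence: it understates it. Second, the trial's decision is not affected: stopping, selection and sample size rest on the tallies alone. In trials that stop at 60, the first-60-patient analysis also gives odds ratios, confidence intervals and p-values, so the LR is not the only evidence reported.

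The opposite reading, that the choice of exponent can never matter for the 8 or 10 benchmarks, is also too strong. It holds without overrun, but the plan puts incomplete-pair data into the proportions, and step 4 shows a result that then crosses 10.

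The percentages assume independent outcomes, exactly 30 per arm at the first look and no overrun. The algebra of the exponent and the generalized-LR values do not depend on the outcome model.

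**What to change.** In the formula, use the observed difference in tallies, X_i − X_j, as the exponent for criterion stops and truncation alike. The fourth power can stay as the special case of a lead of exactly 4.

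In the examples for 60 patients, restate the generalized LRs as 29.9 (20 against 10) and 1.75 (14 against 10).

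The cost is one formula and two numbers. Nothing changes in the design, the stopping rule or the sample size. Reported LRs change only for an analyst who would have applied the fixed exponent literally.

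### The p < 0.05 benchmark of 6.8 is on a different scale from the likelihood ratio it is set beside; at the estimates, the LR > 10 cut-off sits at about p = 0.28

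*Combined protocol and SAP*

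**What the plan says.** All of this is in section VIII, under Formula to Calculate the Likelihood Ratio and its Interpretations, unless stated otherwise.

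- **Definition.** The LR divides the likelihood of the success tallies at (p_i, p_j) by their likelihood "under the assumption that we erred in our selection", that is, with the two values swapped. It equals the odds ratio raised to the power of the lead.
- **Evaluation.** "We will evaluate LR at the maximum likelihood estimates of p_i and p_j", using the adjusted proportions (X + 0.5)/(n + 1).
- **Cut-off and use.** "The LR may offer strong evidence of correct selection (if $LR > 10$) or only weak evidence". The same sentence makes this measure one input to the decision on a phase 3 trial.
- **Benchmarks.** The plan gives 21.5 for a lead of 4 and 46 for tallies of 11 and 6, both at the design rates 0.35 and 0.20. Between these two figures it says "Likelihood ratios in excess of 8 or 10 are generally considered to be moderate to strong evidence" and, as a comparison, that p < 0.05 "corresponds to a LR of only 6.8 in large samples".
- **A second LR.** The next paragraph introduces the LR of the estimates against p1 = p2, calls 14 versus 10 very weak on that measure (1.55), and commits to reporting both LRs.

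**The concern.** Two likelihood ratios with different reference hypotheses are discussed together, and the one figure that links them to a familiar standard is attached to the wrong one. Set after 21.5 and before 46, with the word *only*, the 6.8 invites the reader to conclude that a selected-versus-reversed LR above 10 is a higher bar than p < 0.05. It is a much lower one.

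This matters because the LR is the plan's main evidence statement for the full sample and is to inform whether a phase 3 trial is mounted. Whoever makes that decision could take a result labelled strong as good evidence that the arms differ, when the same tallies are close to uninformative on that question.

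**Working it through.** **Inputs.** Lead of 4 to stop, first decision at 30 per arm, truncation at 50 per arm (Stopping and Decision rule; Table 1). Design rates 0.35 and 0.20 (Study Implementation). LR definition, adjusted proportions and cut-off as above. The 0.05 level is taken as two-sided, z = 1.96.

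**1. The plan's figures reproduce, on two scales.**
- Selected versus reversed, at design values: OR = (0.35/0.65)/(0.20/0.80) = 2.154; 2.154⁴ = 21.5; 2.154⁵ = 46.4.
- Estimates versus p1 = p2, large samples: LR ≈ exp(z²/2) = exp(1.96²/2) = 6.83. This is the plan's 6.8.

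**2. Relation between the scales at the estimates.** Let d be the difference in proportions, n the number per arm, p the pooled proportion and q = 1 − p.
- z² = d²/(2pq/n) = nd²/(2pq).
- Selected versus reversed: log LR = (X_i − X_j) × log OR ≈ nd × d/(pq) = 2z².
- Against equality: log LR ≈ z²/2.

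The first log is four times the second, so the selected-versus-reversed LR is about the fourth power of the LR against equality.

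**3. Benchmarks restated.**
- p = 0.05: exp(2 × 1.96²) ≈ 2,170.
- LR = 10: z = √(ln 10 / 2) = 1.073, two-sided p = 0.283; LR against equality 10^(1/4) = 1.78.

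**4. Exact tallies at 30 per arm** (plan's adjusted proportions for the first LR):

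| Tallies | Selected vs reversed | Against p1 = p2 | Fisher p |
|---|---|---|---|
| 12 vs 8 | 10.2 | 1.83 | 0.41 |
| 8 vs 4 | 24.5 | 2.33 | 0.33 |
| 11 vs 6 | 54 | 2.8 | 0.25 |

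For 8 vs 4: OR = (8.5/22.5)/(4.5/26.5) = 2.225, and 2.225⁴ = 24.5. The largest pooled-z p among all tallies at 30 per arm with LR > 10 is 0.273 (12 vs 8), in line with the large-sample 0.28.

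**5. How often LR > 10 occurs.** I simulated the plan's rule with independent patients, 400,000 trials per case. A separate run of 100,000 matches Table 1: expected size 68.5 (stated 68.4) and correct selection 95.1% (stated 95.1%) in scenario 1; 83.0 and truncation 43.5% (both as stated) in scenario 3.

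| True rates | Selected vs reversed > 10 | Against p1 = p2 > 10 |
|---|---|---|
| 0.35 / 0.20 | 71% | 20% |
| 0.20 / 0.20 | 46% | 3% |

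The lead actually observed was used as the exponent, as in the plan's 46. A fixed exponent of 4 for trials that meet the criterion gives the same exceedance rates. Among trials with LR > 10, about 90% have pooled-z p > 0.05 at 0.20/0.20 and 64% do at 0.35/0.20. At 0.35/0.20, 98% of trials with LR > 10 selected the better arm.

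**The case against.** The best defence is that the LR answers the question the design asks. The label concerns correct selection. Under Analysis of the Primary Endpoint with the Full Sample, the plan disclaims interest in testing equality and says no difference will be declared significant. For its own purpose the label works at the design alternative. The LR is to be taken into account for phase 3, not used as a gate, and readers will also get the LR against equality, plus odds ratios, confidence intervals and p-values for the first 60 patients. All of this stands and limits the point. It does not rescue the 6.8: a design that disclaims significance testing has no need of a p-value benchmark, and one on the wrong scale misleads.

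Several stronger readings might be inferred, and the documents do not support them.

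- *The cut-off of 10 was derived from 6.8.* It rests on the cited convention of 8 or 10; the 6.8 is an added comparison.
- *The plan's 14 versus 10 example contradicts itself.* It is very weak against equality, and its selected-versus-reversed LR is 5.5 (50 per arm) or 8.7 (30 per arm). Both are below 10, so the two labels agree.
- *The 46% is a false-positive rate.* With equal arms the plan treats either selection as acceptable, so it is not an error rate under the plan's objective. It shows only that the label cannot distinguish a difference from none.
- *The cut-off adds nothing to the stopping rule.* That is nearly so only for stops at 60 with low success rates (98.5% exceed 10 at 0.35/0.20). With equal rates it falls to 96% at 0.275 and 68% at 0.50, and only about a third of later stops at the design alternative exceed 10.
- *The 21.5 and 46 equate to particular p-values.* They use fixed design rates; the conversion applies only at the estimates.
- *The label should be moved to the LR against equality.* That needs z = √(2 ln 10) = 2.15, p about 0.03. It would bring a testing standard into a selection design, and is not needed to correct the error.

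**Conclusion.** The point holds. The 6.8 is a correct figure for the LR against equal rates and a wrong comparator for the selected-versus-reversed LR, whose p = 0.05 equivalent at the estimates is about 2,170. A value just above 10 corresponds to a two-sided p of about 0.28 and an LR against equality of about 1.8; larger values have smaller p, so 0.28 marks the boundary and is not typical. The plan does not say how the two LRs are to be weighed when they point to different strengths of evidence, as in 8 versus 4 of 30.

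The z conversions are large-sample approximations, supported by the exact tallies. The frequencies assume independent patients and complete pairs. Clustering within ICU areas is not modelled, and no intracluster correlation is given. The error is in the interpretation of evidence; it does not affect allocation, stopping, selection or the first-60 analysis.

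**What to change.** 1. In the paragraph with the 21.5 and 46 examples, delete the 6.8 comparison. Alternatively restate it on that scale (p = 0.05 is about 2,170 at the estimates; LR = 10 is about p = 0.28) and attach 6.8 only to the LR against p1 = p2.
2. Where the cut-off of 10 is defined, state that LR > 10 is evidence for the selected order over the reversed order, not evidence that the arms differ. State also that the already planned LR against p1 = p2 will be considered alongside it in the phase 3 decision.
3. Add to Table 1, for scenarios 1 to 3, the probability that each LR exceeds 10.

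The cost is a few sentences of SAP text, one simulation, and a less favourable evidence statement. No trial procedure changes.
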